9.2. General Considerations

9.2.1. Definition of Analysis Populations

All randomized subjects will be included in the intent-to-treat (ITT) population. All subjects with at least one application of product in the test phase (i.e. test product for subjects in Group I or sunscreen for subjects in Group II) will be included in the Safety population.

Subjects will be considered eligible for a Per Protocol (PP) population if they were randomized, received at least one application of test product, had at least one post-procedure, post-treatment assessment available and were compliant with both test and washout products post-procedure. Other considerations for eligibility for the PP population including but not limited to use of concomitant medications will be detailed in the Statistical Analysis Plan prior to database unblinding.

9.2.2. Exclusion of Data from Analysis

No data will be excluded from any analyses.

9.2.3. Criteria for Evaluation

The primary evaluation of tolerance will be based on the Dermatologist global assessment. The trial will be considered a success if the majority (i.e. more than 50%) of subjects in the test product group have a favorable Dermatologist global assessment score.

 GlaxoSmithKline	Document Name	GSK-207237-01-001F 20 Day Cream.doc		
	Type	Version	Document Identifier	Effective Date
	eldo_controlled	0.0: Current Effective Date: CURENEW	090032d580e2d8a6	07-Jun-2017 01:32:30
	Reason For Issue	Auto Issue		

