9. STUDY MATERIAL SENSITIVITY TEST
A score of “Severe” for any Dermatologist or Subject Self-Assessed endpoint at any time for the study material sensitivity test.

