5. PRODUCT INFORMATION

5.1. Study Product

The following study products will be supplied by the Clinical Supplies Department, GSKCH:

	Reference / Washout Cleanser	Test Product	Reference / Washout Sunscreen
Product Name	Simple™ Kind to Skin Moisturising Facial Wash	Physiogel Calming Relief SPF 20 Cream	Sunmax Sensitive SPF 50
Product Formulation Code	N/A (Commercial, UK)	CCI [REDACTED]	CCI [REDACTED]
Application Quantity	Approximately 0.6-1 g		
Route of Application	Topical		
Application Instructions	
In your hands, work a small amount into a lather. Massage onto wet skin, rinse with water.
 
Avoid contact with eyes. If contact occurs, rinse thoroughly with water.
 
Apply twice a day (morning and evening)
	
Dispense two pumps of product onto the fingertips and apply to the full face.
 
Avoid contact with eyes. If contact occurs rinse thoroughly with water.
 
Apply twice a day (morning and evening)
 
Do not apply in the morning if you are visiting the site on the same day.
	
Dispense a pea-sized quantity onto the fingertips and apply to the full face.
 
Avoid contact with eyes. If contact occurs rinse thoroughly with water.
 
Apply twice a day (morning and lunchtime)
 
Do not apply in the morning if you are visiting the site on the same day.

 GlaxoSmithKline	Document Name	GSK-207207-01-01-01F 20 Day Cream.doc		
	Type	Version	Document Identifier	Effective Date
	eldo_controlled	0.0: Current Effective Date: Current	090032d580e2d8a6	07-Jun-2017 01:32:30
	Reason For Issue	Auto Issue		

Upon completion of the washout phase, subjects considered to be eligible for the test phase will be randomised to two groups (Group 1: Test product; Group 2: No-treatment) and a qualified dermatologist with experience administering facial peels will conduct the 70% Glycolic Acid procedure.

Subjects randomised to Group 1 will be instructed to apply the test product twice-daily (morning and evening) after cleansing, for a total of 14 consecutive days. All subjects will be instructed to continue using the facial cleanser twice-daily during the morning and evening, and to apply the sunscreen in the morning and at lunchtime. A summary of the subject's post-randomization regimen is included below for clarity.

Randomized Group	Morning	Lunchtime*	Evening
Group 1	1. Cleansing 2. Test Product 3. Sunscreen	2. Sunscreen	1. Cleansing 2. Test Product
Group 2	1. Cleansing 2. Sunscreen	2. Sunscreen	2. Cleansing

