6.8.12. Dermatologist Global Assessment

The Dermatologist will assess the local tolerance of the post-procedure skin care regimen in context of the expected effects of the procedure for each subject using the scale below and document the score on the eCRF. To make this assessment, the Dermatologist will draw on the total set of clinical and subject self-assessment data for each subject. The Dermatologist must be unaware of whether a subject was randomized to test product to protect the blind.

Rating	Description
0 - Product Regimen was Well Tolerated	No clinically significant worsening of the expected signs/symptoms of the procedure. No new signs/symptoms manifest during product use.
1 - Product Regimen was Not Well Tolerated	Clear, clinically relevant worsening of the severity or frequency of expected signs/symptoms of the procedure and/or any occurrence of new, unexpected signs/symptoms during product use.

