9.3.2. Primary Analysis(es)

Descriptive statistics (N, %, 95% confidence intervals) will be used to summarize the proportion of subjects in each product group with a favorable Evaluator global assessment of tolerance. The proportions may also be compared between product groups using Chi-square test, and difference in proportion and 95% confidence interval.

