8.1 Primary Analysis

The primary evaluation of tolerance will be based on the Evaluator (Dermatologist) global assessment. The trial will be considered a success if the majority of subjects in the test product group have a favorable (“well tolerated”) Evaluator global assessment score.

The Dermatologist will assess the local tolerance of the post-procedure skin care regimen in context of the expected effects of the procedure for each subject using the scale below and document the score on the eCRF. To make this assessment, the Dermatologist will draw on the total set of clinical and subject self-assessment data for each subject. The Dermatologist must be unaware of whether a subject was randomized to test product to protect the blind.

Rating	Description
0 - Product Regimen was Well Tolerated	No clinically significant worsening of the expected signs/symptoms of the procedure. No new signs/symptoms manifest during product use.
1 - Product Regimen was Not Well Tolerated	Clear, clinically relevant worsening of the severity or frequency of expected signs/symptoms of the procedure and/or any occurrence of new, unexpected signs/symptoms during product use.

Descriptive statistics (N, percentage, 95% confidence intervals) will be used to summarize the proportion of subjects in each product group with a favorable Evaluator global assessment of tolerance. The proportions will also be compared between product groups using Chi-square test, and difference in proportion and 95% confidence interval.

To visually inspect the treatment effect on dermatologist total score, a plot across time with the raw means will be produced. The plot will display a different symbol for each treatment group.

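### The primary success rule uses the test-arm proportion alone, so the planned difference from the no-product arm cannot change the verdict on the cream

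*Protocol*

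**What the plan says.** **The rule.** Protocol 9.2.3: "The trial will be considered a success if the majority (i.e. more than 50%) of subjects in the test product group" are rated favourably by the dermatologist. SAP 8.1 has the same rule without the percentage: "The trial will be considered a success if the majority of subjects in the test product group have a favorable" rating. Neither contains a term for the no-product group, a margin or a confidence limit.

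**The comparison.** Protocol 9.3.2 makes it optional: "The proportions may also be compared between product groups using Chi-square test, and difference in proportion and 95% confidence interval". SAP 8.1 makes it firm: "The proportions will also be compared between product groups using Chi-square test, and difference in proportion and 95% confidence interval". The Table 9.3.1 template shows both arms, the difference with its interval and the chi-square p-value, and SAP 11 lists it as a topline table. Neither document says what the comparison does to the success verdict.

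**What is rated.** Under Protocol 6.8.12 the dermatologist is to "assess the local tolerance of the post-procedure skin care regimen in context of the expected effects of the procedure". Rating 0 means no clinically significant worsening of the expected effects and no new ones.

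**What the arms share.** Subjects "will be randomised to two groups (Group 1: Test product; Group 2: No-treatment"). The regimen tables in the Protocol (Study Product section) and SAP 3 give both groups the same cleanser and sunscreen after the same peel; the cream is the only planned difference.

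**The concern.** The primary objective (Protocol 2) names the test product, but the success rule reads a rating of the whole regimen in one arm. A favourable rating in Group 1 reflects cleanser, sunscreen and cream together, judged against what the evaluator expects of the peel. The randomised contrast with Group 2 is the part of the design that bears on the cream's own contribution.

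The run-in sharpens this. Exclusion criterion 9 removes anyone with a severe score for any "Dermatologist or Subject Self-Assessed endpoint at any time for the study material sensitivity test". That test applies peel, neutraliser and sunscreen to the forearm (Protocol 6.1.8), and the washout then has everyone use cleanser and sunscreen for seven days. The cream is not tried before randomisation. A high favourable rate in Group 2 is therefore plausible, though not stated, and a 50% bar in Group 1 would then say little about the cream.

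At stake is a declared success that the trial's own randomised data contradict.

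**Working it through.** **1. The plan's own figure.** The only power statement concerns TEWL. With n = 30 and 2.1/4 = 0.525 SD (SAP 4), a one-sample t-test at two-sided 0.05 has 79.4% power, which agrees with the stated 80%. It gives no assurance about the tolerance rating, for which the documents give no expected rate, margin or power.

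**2. Inputs.** 80 randomised and about 30 completers per group (Protocol 9.1). The rating is made only at Visit 8, so about 30 per arm would be rated. I take rated subjects as the denominator. The Table 9.3.1 footnote bases percentages on all subjects in the group, so I also show 40 per arm (80/2, equal allocation assumed), all rated. Success needs at least 16/30 or 21/40.

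**3. A result that passes the rule.** Test 16/30 = 0.533, control 27/30 = 0.900.

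- Difference: 0.533 - 0.900 = -0.367.
- Wald SE: sqrt(0.533 × 0.467/30 + 0.9 × 0.1/30) = sqrt(0.00830 + 0.00300) = 0.1063.
- 95% CI: -0.367 ± 1.96 × 0.1063 = -57.5 to -15.8 points. The Newcombe interval is -55.1 to -14.0.
- Chi-square: pooled proportion 43/60 = 0.717; variance 0.717 × 0.283 × 2/30 = 0.01354; 0.367²/0.01354 = 9.93; p = 0.0016.

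With 40 rated per arm, 21/40 against 38/40 is a success at -42.5 points (Wald -59.4 to -25.6; p = 0.00002). If the control result is 27/30, every test result from 16/30 to 20/30 is both a success and significantly worse by chi-square. If it is 30/30, this holds from 16/30 to 26/30. These examples need no assumed rates.

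**4. How often, under assumed true rates.** Let X and Y be independent Binomial(30) counts for test and control. P(success) = P(X ≥ 16), which does not depend on the control rate. The joint probability sums P(X = x)P(Y = y) over x ≥ 16 and all y for which the upper 95% limit of the difference is below zero.

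| True rate, test / control (assumed) | P(success) | Success with Wald CI below 0 | Success with Newcombe CI below 0 |
|---|---|---|---|
| 65% / 95% | 93% | 83% | 80% |
| 70% / 90% | 98% | 52% | 47% |
| 90% / 95% | about 100% | 10% | 5% |
| 90% / 90% | about 100% | 2.8% | 1.3% |
| 95% / 95% | about 100% | 1.4% | 0.4% |

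With 40 rated per arm, success and the Wald joint figure are 96% and 92% for 65%/95%, and 99% and 63% for 70%/90%. The last two table rows give the cost of an added condition when the cream makes no difference.

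**5. The interval method matters.** For 36/40 against 40/40, the Wald upper limit is -0.7 points and the Newcombe upper limit is +0.6. The documents name no method.

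**6. What an added condition would not do.** At assumed rates of 80% and 95% with n = 30, success would still be declared in about 54% of trials with Wald (99.98% - 46.2%) and about 64% with Newcombe (99.98% - 36.4%). A non-inferiority claim is a different task: for an assumed 15-point margin, 90% in both arms, one-sided 0.025 and 80% power, n per arm = (1.96 + 0.842)² × 2 × 0.9 × 0.1/0.15² = 63.

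**The case against.** A reader might infer that the stated objective goes unanswered, or that the rule gives a wrong answer even without sampling error. The documents do not support that. The primary objective and the hypothesis in the synopsis are non-comparative: tolerance of the product in peeled subjects, and a favourable profile in that population. Comparison between groups is a separate secondary objective. The rule answers the question as posed for the regimen; the gap opens when its result is read as a statement about the cream.

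A reader might also infer that the trial disregards its control arm. Only the rule does. The SAP commits to the comparison, and a deficit would sit in the same topline table as the verdict. The documents attach no stated consequence to success.

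Three further points stand. The scale is anchored to the expected peel effects, so the test-arm proportion is not simply the peel's natural course, although an evaluator's judgement does not replace a control. The contrast is not a pure measure of the cream either: subjects are not blinded, and the rating draws on their self-assessments. And no document gives a tolerance rate; Protocol 3.4 cites favourable tolerance data, and at 90% against 95% the conflict is uncommon.

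What survives is that the verdict is prespecified and the comparison, however visible, cannot alter it.

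**Conclusion.** The point holds in limited form. Protocol 9.2.3 and SAP 8.1 let the test-arm proportion alone decide success, so a success can coexist with a clear randomised deficit; 16/30 against 27/30 shows this without assumed rates. How often it would happen rests on assumed true rates, independent arms, 30 rated per arm and the interval method: from about 10% of trials (90%/95%) to 83% (65%/95%) with Wald. The larger figures describe a cream that causes a 20- to 30-point deficit, which nothing in the documents predicts. This is a cheap improvement to how the conclusion is drawn, not a failure of the trial to address its objective.

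**What to change.** In Protocol 9.2.3 and SAP 8.1:

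- Keep the more-than-50% condition as the criterion for the regimen.
- State that any conclusion about the cream rests on the Table 9.3.1 difference (test minus no test product).
- Do not declare the cream well tolerated if the 95% CI for that difference lies wholly below zero. Name a small-sample method such as Newcombe, and say that this interval governs if it disagrees with the chi-square test.
- In Protocol 9.3.2, make the comparison definite rather than optional, to match the SAP.

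Cost: no new data or tables. If the arms are truly equal, the condition blocks success in about 0.4% to 1.3% of trials with Newcombe, or 1.4% to 2.8% with Wald, at n = 30 and common rates of 95% and 90%. Changing a success criterion may need a protocol amendment and, if classed as substantial, ethics committee approval; it should be settled before unblinding. The text should say that the condition guards against a demonstrated deficit and does not establish non-inferiority.

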9.2.4. Criteria for Assessing Efficacy

Efficacy measurements in this study will be based on changes from baseline in TEWL and Corneometer values at each visit. The baseline for these measurements will be defined as the measurements made 60±15 minutes after the facial peel procedure, before any test product application. Differences between product groups will also be explored.

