2. OBJECTIVE(S) AND ENDPOINT(S)

Objective(s)	Endpoint(s)
Primary	
Assessment of the local tolerance of the test product in subjects who have undergone a 70% Glycolic Acid facial peel	Evaluator (Dermatologist) global assessment of tolerance
Secondary	
Assessment of skin recovery (change from baseline) over a period of 14 days in subjects who have undergone a 70% Glycolic Acid facial peel	
Combined (sum of) Evaluator (Dermatologist) scores for signs/symptoms of erythema, edema, desquamation and dryness
 
Individual Evaluator (Dermatologist) scores for erythema, edema, desquamation and dryness
 
Combined (sum of) subject self-assessment scores for redness, pain, stinging/burning, itching, tightness and dryness
 
Individual subject self-assessment scores for redness, pain, stinging/burning, itching, tightness and dryness
 
Instrumental measurement of barrier function (Tewameter) and moisturisation (Corneometer)
 
Subject global self-assessment

Assessment of skin recovery (change from baseline) between treatment groups.	All assessments and measurements listed above

 GlaxoSmithKline	Document Name	GSK267237/21308F 20 Day Cream.doc		
	Type	Version	Document Identifier	Effective Date
	eldo_controlled	0.0: Current Effective/Current	090032d580e2d816	07-Jun-2017 01:32:30
	Reason For Issue	Auto Issue		

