Schalka (2013) published the results of a clinical study which investigated the efficacy and safety of a novel cosmetic skin care product in subjects who underwent a 5% retinoic acid facial peel. This comparative, open-label clinical study randomized 52 subjects who were divided into two groups, with 26 subjects allocated to each group. One group was provided with a Sun Protection Factor (SPF) 30 cream (control) and the other group was provided with the test product and SPF 30 control. Regular clinical assessment and biophysical measurements were conducted for a

 GlaxoSmithKline	Document Name	090032d580e2d8a6 20 Day Cream.doc		
	Type	Version	Document Identifier	Effective Date
	eldo_controlled	0.0; Current Effective	090032d580e2d8a6	07-Jun-2017 01:32:30
	Reason For Issue	Auto Issue		

period of 1 week post-procedure. Fifty subjects completed the study, with one subject withdrawing for personal reasons and the other discontinued from the study due to the occurrence of mild contact dermatitis in the test product plus sunscreen group. Statistically significant ($p \leq 0.05$) cosmetic benefits were observed for clinically-assessed desquamation (Days 4 to 7) and instrumental Corneometer measurements (Days 2 to 4) for the treatment group over the control group. Crucially, the magnitude of cosmetic assessments between groups was numerically largest between days 2 and 4, presumably because the skin's natural repair processes were continually reducing the cutaneous damage for both groups, making it more difficult to measure a cosmetic benefit over time. Barrier function was observed to gradually worsen over the duration of the study, with weak indications of improvement between days 4 and 7. There was no statistically significant barrier function benefit between groups at any time point.

Based on this literature review, subject visits have been included at 24-72 hours post-procedure, where differences between control and test groups are expected to be largest. While it is expected the skin's barrier function will return to normal 24 to 48 hours following the procedure, the total duration of the test phase is 14 days to enable sufficient time to monitor desquamation and erythema compared to the post-procedure, pre-treatment baseline.

 GlaxoSmithKline	Document Name	GSK-207237-01-001F 20 Day Cream.doc		
	Type	Version	Document Identifier	Effective Date
	eldo_controlled	0.0: Current Effective/Current	090032d580e2d8a6	07-Jun-2017 01:32:30

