	Combined (sum of) subject self-assessment scores for redness, pain, stinging/burning, itching, tightness and dryness
	Individual subject self-assessment scores for redness, pain, stinging/burning, itching, tightness and dryness
	Instrumental measurement of barrier function (Tewameter) and moisturisation (Corneometer)
Subject global self-assessment	
Assessment of skin recovery (change from baseline) between treatment groups.	All assessments and measurements listed above

3 Study Design

- Evaluator-blind

- Single study center
- Parallel-group
- Healthy female subjects with moderate to advanced photo-damaged facial skin
- Single test product (Physiogel Calming Relief SPF 20 Cream) used in combination with commercial sunscreen (“washout product”, Sunmax Sensitive SPF 50). All subjects were to use the commercial sunscreen and cleanser provided. Randomization was to two groups (test product, no test product) with product usage as shown in the table below:

Randomized Group	Morning	Lunchtime*	Evening
Group 1 (Test product)	1. Cleansing 2. Test Product 3. Sunscreen	1. Sunscreen	1. Cleansing 2. Test Product
Group 2 (No test product)	1. Cleansing 2. Sunscreen	1. Sunscreen	1. Cleansing

*Lunchtime application must be at least 3 hours after previous sunscreen application

4 Sample Size Determination

Approximately 130 healthy females within the ages of 30 and 60 years (inclusive) with Fitzpatrick Skin Classification II-IV and moderate to advanced photo-damaged skin will be screened to randomize 80 subjects to ensure approximately 60 subjects (30 subjects per group) successfully complete the study.

The sample size is based on clinical considerations and literature precedent [Narurkar, Schalka, Sulimovic, Kim]. With 30 subjects per treatment group, a change from baseline in Transepidermal Water Loss (TEWL) at least half the magnitude of the standard deviation (e.g. assume $std=4$ (ref. RH02030 after 2D strip), and 2.1 point mean change from baseline) can be detected at two-sided $\alpha=0.05$ with 80% power.

5 Data Considerations

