8.2 Secondary Analysis

Efficacy measurements in this study will be based on changes from baseline in TEWL and Corneometer values at each timepoint. Both measurements will be assessed pre-procedure and at Baseline (60±15 minutes post-procedure), 180 minutes post-procedure, 360 minutes post-procedure, and 1, 2, 3, 7 and 14 days post-procedure. The baseline for these measurements will be defined as the measurements made 60±15 minutes after the facial peel procedure, before any test product application.

Secondary assessments of local tolerance will be based on Evaluator (Dermatologist) and Subject self-assessment scores at each timepoint and reported adverse events. The baseline for these assessments will be defined as the assessments made 60±15 minutes after the facial peel procedure, before any test product application.

Evaluator and Subject assessment scores will be tabulated at each timepoint (Baseline (60±15 minutes post-procedure), 180 minutes post-procedure, and 1, 2, 3, 7 and 14 days post-procedure) for each product group descriptively as the number and percentage of subjects with each rating score for each assessment (none, mild, moderate or severe).

Changes from baseline in the Evaluator and Subject self-assessment and instrumental endpoints (TEWL and corneometry) will be tabulated by product group and timepoint and summarized descriptively using means, standard deviations and 95% confidence intervals and assessed for significance (different from zero) using t-tests or Wilcoxon signed rank tests dependent upon the distribution of the data.

Differences between product groups in the mean changes from baseline in Evaluator, and Subject self-assessment and instrumental endpoints will also be explored using t-tests or Wilcoxon rank sum tests at each timepoint and summarised using 95% confidence intervals.

If sufficient data is not available for formal analyses for individual scores, summary stats and frequency counts will be presented.

To visually inspect the treatment effect on subject self-assessment total scores, a plot

across time with the raw means will be produced. The plot will display a different symbol for each treatment group.

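### TEWL and Corneometer: nothing states that product efficacy rests on the between-group difference rather than on each arm's change from the post-peel baseline, and the stated 80% power covers only the latter

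*Protocol*

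**What the plan says.** Protocol 9.2.4, the section on efficacy criteria, states: "Efficacy measurements in this study will be based on changes from baseline in TEWL and Corneometer values at each visit". It defines baseline as the reading 60±15 minutes after the peel and before any test product, then adds: "Differences between product groups will also be explored". SAP 8.2 repeats this structure.

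Two analyses of the change follow (Protocol 9.3.3, SAP 8.2):

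- **Within each arm.** The change at each timepoint is "assessed for significance (different from zero) using t-tests or Wilcoxon signed rank tests dependent upon the distribution of the data".
- **Between arms.** Mean changes are compared by t-test or Wilcoxon rank sum test with 95% confidence intervals, again described as explored. The SAP Appendix 3 template for Table 9.3.3.2.1, also used for TEWL and Corneometer, has a row for the group difference with its interval and p-value.

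Both match stated secondary objectives in Protocol 2: skin recovery over 14 days, and "Assessment of skin recovery (change from baseline) between treatment groups".

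SAP 4 states the power for "a change from baseline in Transepidermal Water Loss (TEWL) at least half the magnitude of the standard deviation", with 30 per group, two-sided alpha 0.05 and 80% power. Its example is an SD of 4 and a mean change of 2.1. The same section says that the sample size rests on clinical considerations and precedent.

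**The concern.** The study is designed to evaluate cosmetic efficacy as well as tolerance (Protocol 3.1), so a reader will look to TEWL and Corneometer for a statement about the product. The plan yields two kinds of p-value for that purpose and does not say which one counts.

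The within-arm test cannot do the job. Baseline is read shortly after an acid peel, and Protocol 3.4 expects that "barrier function will return to normal 24 to 48 hours following the procedure", without reference to the product. It also attributes falling skin damage in both groups of a cited retinoic acid peel study to natural repair. Barrier function in that study gradually worsened, so even the direction of the natural course is uncertain. Either way, the test arm can move from baseline with no help from the product. Only the randomized contrast with no test product separates the two.

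The stakes are a product statement built on recovery that both arms share, and an 80% figure taken as power for a comparison it does not describe.

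**Working it through.** **Inputs.** From SAP 4: 30 per group, SD 4, mean change 2.1, two-sided alpha 0.05, stated power 80%. Assumed: equal allocation, and SD 4 as the SD of change in both arms (relaxed in step 4). The natural change is not given, so a range is shown. All of this concerns TEWL; the documents give no SD for Corneometer.

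**1. Reproducing the 80%.** Standardized change d = 2.1/4 = 0.525.

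- One-sample t-test, n = 30: noncentrality d√n = 0.525 × √30 = 2.88, 29 df, power **79.4%**.
- Two-sample t-test, 30 per arm: noncentrality d√(n/2) = 0.525 × √15 = 2.03, 58 df, power **51.6%**.

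The plan's figure matches the one-sample test of change against zero and not the comparison of arms.

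**2. What the within-arm test does when the product does nothing.** Both arms are given the same change, with SD 4 and n = 30, at a single timepoint:

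| Common change (units, assumed) | Test arm significant against zero | Between-group test significant |
|---|---|---|
| 0 | 5% | 5% |
| 0.5 | 10% | 5% |
| 1 | 26% | 5% |
| 2.1 | 79% | 5% |
| 3 | 98% | 5% |

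A simulation at 2.1 units (20,000 trials) agreed: 79% in the test arm, 80% in the control arm, 4.8% between arms. In 16% of trials the test arm was significant and the control arm was not, although the arms did not differ.

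**3. What the between-group comparison can detect.** At 80% power:

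- 30 per arm: 0.736 SD, or 0.736 × 4 = 2.94 units.
- 40 per arm (all 80 randomized analysed): 0.634 SD, or 2.54 units. Power for 2.1 units is then 64.0%.

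The 95% interval for the difference has half-width t(0.975, 58) × 4 × √(2/30) = 2.00 × 4 × 0.258 = 2.07 units at 30 per arm.

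**4. If SD 4 is a single-visit SD.** SAP 4 does not say which SD it is. With baseline correlation r, the SD of change is 4√(2(1−r)):

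- r = 0.3: SD 4.73, between-group power for 2.1 units 39%.
- r = 0.5: SD 4.00, power 52%.
- r = 0.7: SD 3.10, power 73%.

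**5. Gain from using baseline as a covariate.** Holding the SD of change at 4, with equal variances at baseline and follow-up, the ANCOVA residual SD is 4√((1+r)/2). For r = 0.3, 0.5 and 0.7 that is 3.22, 3.46 and 3.69. With one further df lost, power for 2.1 units is 70%, 64% and 58% at 30 per arm, against 52% unadjusted. At 40 per arm it is 82%, 76% and 71%, against 64%.

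**6. Several timepoints.** SAP 8.2 lists seven after baseline (180 and 360 minutes; 1, 2, 3, 7 and 14 days). With no product effect and an assumed common correlation of 0.7 to 0.3 between timepoints, at least one between-group p below 0.05 occurs in about 18-27% of trials per instrument.

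**The case against.** The strongest reply is that the plan already contains the right comparison. Measuring efficacy by change from baseline names a variable, and the between-group test uses that same variable. The comparison is a listed objective with a test, an interval and a table row beside the within-arm results, so a reader of the table would see both arms moving together. All of this stands. It rules out two inferences: that the randomized comparison is missing, and that the documents treat a significant within-arm change as proof of efficacy. No section says the latter, and no TEWL or Corneometer success rule exists.

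The within-arm tests also answer a real objective, recovery over 14 days, and should stay. Nor is SAP 4's 80% an error: its wording is about change from baseline, and for that it is correct.

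Nor do the documents show that between-group differences are generally out of reach. In the cited retinoic acid peel study, with 26 per group, the protocol reports "There was no statistically significant barrier function benefit between groups at any time point", but also a significant between-group Corneometer benefit on Days 2 to 4. The null barrier result may reflect no effect rather than a missed one.

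What the reply does not supply is a sentence ranking the two analyses, a power figure for the group difference, or use of the baseline reading as a covariate.

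**Conclusion.** The point holds as a gap in stated interpretation. The plan does not say that a product efficacy statement on TEWL or Corneometer rests on the between-group difference, although by its own reasoning on recovery the within-arm change cannot carry one. With no product effect and an assumed common change of 2.1 units, the within-arm test is significant 79% of the time, against 5% between arms. The 79% falls to 10% if the common change is 0.5 units and rises to 98% at 3 units.

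The 80% in SAP 4 holds for within-group change only. For a 2.1-unit group difference at 30 per arm, power is about 52% if SD 4 is the SD of change, or about 39-73% if it is a single-visit SD with baseline correlation 0.3-0.7.

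The consequence is limited. These are secondary endpoints, and trial success depends on the Dermatologist global assessment (Protocol 9.2.3, SAP 8.1). A reader might infer that the trial is underpowered for its purpose and needs more subjects. The documents do not support that, because the sample size is not derived from a between-group TEWL difference.

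**What to change.** In Protocol 9.2.4 and 9.3.3 and SAP 8.2, before unblinding, add:

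> Statements on product efficacy for TEWL and Corneometer rest on the between-group difference at each timepoint, estimated by ANCOVA with the 60-minute baseline as covariate, with 95% CI (rank-based ANCOVA or the planned rank sum test if the data are clearly non-normal). Within-group tests describe skin recovery and are not evidence of a product effect. Between-group p-values across the seven post-baseline timepoints are not adjusted for multiplicity and are exploratory.

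In SAP 4, add:

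> The 80% refers to the within-group change. If SD 4 is the SD of change, 30 per group detects a between-group difference of 0.74 SD (2.94 units) with 80% power before baseline adjustment.

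Naming one key timepoint before unblinding is optional. Protocol 3.4 points to 24-72 hours, "where differences between control and test groups are expected to be largest", but it also expects barrier function to be back to normal by 24 to 48 hours, so a late choice may leave little TEWL difference to find.

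Keep the sample size and the within-group tests. The cost is wording in four sections and one ANCOVA per instrument and timepoint; no subjects or visits are added, and the table template already has the row. The downside is that an efficacy statement becomes harder to reach: at 30 per arm, with SD of change 4, power at a given timepoint for a 2.1-unit effect is 58-70% with ANCOVA (baseline correlation 0.7-0.3).
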